11.1.1 Reporting of AEs

A database of all AESI will be maintained in REDCap™. Adverse events which are not an AESI will not be collected. The event will be categorized by organ system, relationship to treatment, its grade of severity, and resolution. The PI and study statistician will periodically review the collective adverse events with the intention of identifying any trends or patterns in toxicity. If any such trends are identified, depending on their severity and frequency, a protocol amendment will be considered.

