7.1.4 Adverse Events of Special Interest (AESI)

The occurrence of adverse events of special interest (AESIs) will be recorded only for the 30-day post-procedure phase.

AESIs for this study will be graded using the National Cancer Institute's (NIH) Common Terminology Criteria for Adverse Events (CTCAE) v4 and are the following: any grade of seizure, dizziness, somnolence, cognitive

disturbance, nausea, vomiting, ataxia, nystagmus, suicidal ideation, suicide attempt, anxiety, irritability, depression, psychosis and personality change (e.g. aggression).

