10.2 Study Period

Day 0 and prior (diagnosis): occurring at least within 48 hours prior to MSR

- Randomization
- Initiate AED, per Section [7.1.1](#) (LCM 100mg BID or LEV 1000mg BID)
- Characterize seizure type, if applicable, (i.e., simple partial, complex partial, or generalized)

Week 0-6

- Management of AEDs for any seizure events or adverse events will be left at the discretion of the treating physician. If side effects occur, adjusting dosing of current AED before changing AEDs is recommended.

Week 6-10: at the first planned post-procedure visit (LGG or brain metastasis) or first visit after radiation (HGG), the following study endpoint data will be collected only for the 30-day post-procedure time period

- Collection of calendar, if not already obtained from the REDcap database
- CMP and CBC with differential to assess resolution of toxicity
- AESI (please see Section [7.1.4](#))
- Number of readmissions, ED visits, provider communications during the 30-day post-procedure phase
- Number of dose adjustments, additions or discontinuations of AED(s) during the 30-day post-procedure phase
- Initiate weaning of the AED per discretion of the treating physician, for example:
 - LCM 100/50mg x1 week, 50/50mg x 1 week, 50mg daily x 1 week, then off
 - LEV 1000/500mg x1 week, 500/500mg x 1 week, 500mg daily x 1 week, then off

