10.6 Study Assessments

Study assessments listed here are obtained per standard of care and are only documented for purposes of eligibility assessment.

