11.1 Adverse Events

An AE is any untoward medical occurrence in a subject receiving study drug and which does not necessarily have a causal relationship with this treatment. An AE can therefore be any unfavorable and unintended or worsening sign (including an abnormal laboratory finding) or symptom temporally associated with the use of the AED, whether or not related to use of the AED.

From the time the subject initiates AED therapy through the time the subject is off study (as defined in Section [7.3](#)), all AESIs must be recorded in the REDCap™ database AE electronic Case Report Form (eCRF). Adverse events which are not an AESI will not be collected.

AESIs will be assessed according to the Common Terminology Criteria for Adverse Events (CTCAE) version 4. If CTCAE grading does not exist for an AESI, the severity of the AESI will be graded as mild (1), moderate (2), severe (3), life-threatening (4), or fatal (5).

Attribution of AEs will be indicated as follows:

- Definite: The AE is clearly related to the study drug
- Probably: The AE is likely related to the study drug
- Possible: The AE may be related to the study drug
- Unlikely: The AE is doubtfully related to the study drug
- Unrelated: The AE is clearly NOT related to the study drug

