11.2 Serious Adverse Events

An AE is considered “serious” if in the opinion of the investigator it is one of the following outcomes:

- Fatal
- Life-threatening
- Constitutes a congenital anomaly or birth defect

- A medically significant condition (defined as an event that compromises subject safety or may require medical or surgical intervention to prevent one of the three outcomes above).
- Requires inpatient hospitalization or prolongation of existing hospitalization
- Results in persistent or significant incapacity or substantial disruption to conduct normal life functions.

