11.2.1 Reporting of SAEs

All serious and unexpected adverse events should be reported immediately to [name] (page [contact] or her designee [contact])). Only adverse events that the Duke Sponsor-Investigator determines to be serious, unanticipated, and related or possibly/probably (i.e. more likely than not) related to the research must be reported to the Duke IRB. Those adverse events will be submitted in the electronic IRB (eIRB) system, according the following guidelines:

- Report within 24 hours of learning about any subject's death that was unanticipated and more likely related to the research than unrelated;
- Report within 5 business days of learning about any serious, unanticipated, and related or possibly/probably related adverse event;
- Report within 10 business day of learning about any other unanticipated problem or event that was more likely related to the research than unrelated.

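### The AESI-only collection rule makes no exception for serious events, so the trend review and the section 13.5 tables cannot show non-AESI SAEs by arm

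*Protocol*

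**What the plan says.** Protocol section 11.1 defines adverse events, requires AESIs to be entered in the REDCap AE form, and says that other events are not collected. Section 11.1.1 repeats the rule: "Adverse events which are not an AESI will not be collected". It then has the PI and the statistician review the collected events periodically for toxicity trends. Section 13.5 builds its grade tables from AESIs and compares the percentage of patients with any AESI across the three arms.

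The protocol also treats serious events as a separate class. Section 11 makes the PI responsible for identifying and documenting SAEs as well as AEs. Section 11.2 lists the criteria for seriousness, among them "Requires inpatient hospitalization or prolongation of existing hospitalization". Section 11.2.1 begins "All serious and unexpected adverse events should be reported immediately to" and names a study contact; it does not limit this to AESIs.

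On laboratory tests, section 10.2 lists for the week 6-10 visit "CMP and CBC with differential to assess resolution of toxicity". Section 10.6, which covers the same tests, says "Study assessments listed here are obtained per standard of care and are only documented for purposes of eligibility assessment". The Table 2 footnote limits recorded endpoint data to the first 30 days after the procedure.

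**The concern.** Safety and tolerability of LCM and LEV is the protocol's only secondary objective, and section 5.2.9 intends the side-effect results to feed a risk-benefit judgement on prophylaxis. The AESI list was fixed in advance and is mainly neurological, behavioural and gastrointestinal. A serious renal, hepatic, haematological, cardiac or allergic event is not on it.

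Randomization makes it possible to compare the frequency of serious events between arms without relying on a case-by-case judgement of cause. That comparison needs every SAE, in every arm, in one dataset. As worded, the rule removes non-AESI SAEs from that dataset, although the same chapter requires the PI to document them.

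**Working it through.** No figure in the plan is at issue, so the check is mainly a comparison of sections.

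**1. Is there an exception for serious events?** Sections 11.1 and 11.1.1 state the exclusion without qualification. The seriousness criteria come later, in 11.2, and do not refer back to it. The requirement in 11.2.1 concerns notification; it specifies no form or dataset. Section 11 requires SAEs to be documented but does not say where. The rule therefore covers SAEs as written.

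**2. What does the AESI list cover?** Section 7.1.4 has 15 terms: seizure, dizziness, somnolence, cognitive disturbance, nausea, vomiting, ataxia, nystagmus, suicidal ideation, suicide attempt, anxiety, irritability, depression, psychosis and personality change. None is a laboratory, renal, hepatic, haematological, cardiac or allergic term.

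**3. Where else could a non-AESI serious event appear?**

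| Route | What it holds | What it lacks |
|---|---|---|
| 11.2.1 | Individual reports of serious unexpected events; those judged related go to the IRB | A dataset or count by arm; serious events judged expected |
| 12.1 | Quarterly review of safety events; charts of 20% of subjects | A comparison of arms |
| 7.1.3 | Reasons for readmissions and ED visits within 30 days | Grade and attribution |
| 13.6.1 | Reasons for a long initial stay, by group | Grade and attribution |
| 13.4.2, 13.4.3 | Readmission, ED visit or death, as a percentage within each group | Separation of deaths and SAEs from the composite |

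No route gives a graded, attributed tabulation of non-AESI SAEs by arm. SAP sections 6 and 7 define no SAE, death or laboratory variable. The analysis part of the SAP was not available for this review, so nothing is claimed about it.

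**4. Is Arm C covered?** Section 11.1 defines an AE as occurring in a subject on study drug, starts recording at AED initiation, and attributes events only to study drug. Arm C has no AED initiation, so no start of recording is defined for it, yet 13.5 compares all three arms. Section 11.1 also records AESIs until the subject is off study, whereas 7.1.4 stops at 30 days.

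**5. Scale.** The 1:1:2 allocation of 232 patients (13.8) gives 232/4 = 58 on LCM, 58 on LEV and 116 on no AED, hence 116 on either drug. The documents give no rate for non-AESI serious harm, so the rates below are assumptions. The chance of at least one event is 1 − (1 − p)^n.

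| Assumed true rate p | One drug arm, n = 58 | Both drug arms, n = 116 |
|---|---|---|
| 1% | 44% | 69% |
| 2% | 69% | 90% |
| 3% | 83% | 97% |
| 5% | 95% | 99.7% |

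If such events were collected and none occurred, the exact one-sided 95% upper bound, 1 − 0.05^(1/n), would be 5.0% for n = 58 and 2.5% for n = 116. Under the AESI-only rule the AE database supports neither a count nor a bound.

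**6. Laboratory tests.** Week 6 is day 42, which is after day 30. Section 10.2 nevertheless lists the CBC and CMP under data collected only for the 30-day period. Section 10.6.3 takes its timing from Table 2, which schedules both tests at follow-up, so the eligibility-only statement in 10.6 also covers a draw that cannot serve eligibility. No laboratory analysis appears in section 13.

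**The case against.** The restriction looks deliberate. It is stated twice, section 7.2 describes the dosing as standard and FDA-approved, and the secondary endpoint is itself the AESI percentage. Expedited reporting and the AE database are separate systems, so 11.2.1 may properly cover events the database does not hold. This stands: limiting *non-serious* events to a list is a reasonable choice, and the fix leaves it in place. It does not explain why SAEs, which the PI must document, should have no place in the database.

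Three stronger readings are tempting, and the documents do not support them.

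- *The trial cannot see unexpected harm.* Serious unexpected events must be reported at once whether or not they are AESIs, the PI monitors events continuously, and safety events are reviewed quarterly. Only the aggregate view by arm is missing.
- *A drug would look safer than it was.* A serious event that leads to an ED visit or readmission within 30 days counts in the primary endpoint whatever its cause. So does a death that prevents completion of the 30 days. The percentage is calculated within each treatment group, so an excess on one drug would count there.
- *Every readmission is an SAE that goes unrecorded, and the design rates give the number.* Those rates imply 116 × 0.12 = 13.9 and 116 × 0.25 = 29.0, or about 43 patients with a primary event. But the documents do not split ED visits from readmissions, 11.2 leaves seriousness to the investigator's opinion, and readmissions caused by an AESI are recorded. On the literal definition in 11.1, only the roughly 14 patients in the drug arms could have an AE at all. No count of lost SAEs follows.

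The laboratory part is also limited. The Table 2 footnote concerns endpoint data, and laboratory values are not an endpoint in Table 1. The draw falls after the 30-day window and, for newly diagnosed or transformed high-grade tumours, after radiation and temozolomide, so it would say little about the AEDs.

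**Conclusion.** The point holds in a limited form. Followed as written, sections 11.1 and 11.1.1 keep non-AESI SAEs out of the AE database, so neither the periodic trend review nor the 13.5 tables can show them by arm with grade and attribution. This sits badly with the PI's duty in section 11 to document SAEs and with safety being the only secondary objective. The other routes capture individual cases or the composite; they do not replace that table.

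The number of events affected cannot be derived from the documents. The detection probabilities above rest on assumed rates and are for scale only. The conclusion rests on the wording of the protocol and assumes that no separate SAE dataset exists outside these documents. This is an inexpensive improvement to a stated rule; it does not affect the validity of the primary comparison. The laboratory statements need only to be made consistent.

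**What to change.** - **Sections 11.1 and 11.1.1.** Replace the exclusion with: *Only non-serious events outside the AESI list are exempt from collection. All SAEs are entered in the REDCap AE eCRF in all three arms, from randomization through the 30-day post-procedure period, with grade, outcome and, in the drug arms, attribution to study drug.*
- **Section 11.1.** Amend the AE definition and the start of recording so that Arm C is covered, and align the end of AESI recording with 7.1.4.
- **Section 13.5.** Add a table of SAEs and deaths by arm (LCM, LEV, no AED), with a matching entry in the SAP, and include SAEs in the periodic review under 11.1.1.
- **Sections 10.2, 10.6 and the Table 2 footnote.** State consistently whether the week 6-10 CBC and CMP results are recorded, and for what purpose.

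The cost is amendment wording, one SAE form and modest extra data entry, including surgery-related SAEs unrelated to the AEDs. No new procedure is needed. The SAP describes randomization in the past tense. If conduct is complete, SAEs could be sought from hospital records where these allow; otherwise the report should state that non-AESI SAEs were not systematically collected.

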5.2.5 Adverse Events

Lacosamide. LCM's most common adverse events (AEs) based on phase IIB/III trials in partial-onset seizures were related to central nervous system (CNS) and gastrointestinal effects^{39,40}. Dizziness, headache, nausea and diplopia were the most common in a pooled analyses of the trials, occurring at ≥10% in all doses combined (200-600mg/day, N=944)⁴¹. Other less common AEs included nystagmus, ataxia, vomiting, fatigue, somnolence, and headache^{39,40,42}. Incidence appeared dose related, more apparent during the initial titration phase, and less frequent during the maintenance phase¹⁴. The most common AEs that led to discontinuation of the drug were dizziness and abnormal coordination, and these occurred at the higher dose of 600mg/day⁴². There were no serious safety concerns regarding hematologic or clinical chemistry values identified⁴². Moreover, another meta-analysis of 10 randomized controlled trials of LCM for various indications determined LCM was not associated with any apparent adverse effect on cognition⁴³.

Levetiracetam. LEV is well tolerated; however, it can cause behavioral AEs such as aggression, irritability, and anger, as well as somnolence and cognitive side effects. Behavioral AEs reportedly occur in approximately 13% of patients, but up to 30% for some AEs such as irritability or anxiety⁴⁴. It has been associated with suicidal tendency and has a contraindication for use in patients with past history of psychiatric illness⁴⁵.

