5.2.7 Efficacy in Brain Tumors

Seizures associated with brain tumors belong to the category of POS, either with or without secondary generalization⁶³. Since it is relatively new, there is limited data on LCM in brain tumors. Current data supports its tolerability and efficacy as an add-on agent⁶⁴. One retrospective analysis of 70 patients with primary brain tumors reported a decrease in seizure frequency in 66% (47/70) of patients⁶⁵. There are currently ongoing randomized, double-blind, placebo-controlled trials of LCM for seizure prophylaxis in patients with high grade gliomas (NCT01432171), and one as adjunctive therapy to refractory epilepsy in patients with low grade glioma (LGG) (NCT02276053). Its related side effects are the same as in non-brain tumor patients, mainly dizziness at high doses⁶⁵.

LEV, on the other hand, has evidence to support its use as a first line agent in brain tumors, due to its efficacy, low drug-drug interactions, and tolerability⁶⁶⁻⁶⁸. Seizure freedom with LEV has ranged from 76-91% with seizure reduction by half in 100% of patients^{3,67-69}. Recent studies have also shown it has a potential anti-tumor effect as an added benefit secondary to its role as an MGMT inhibitor, although this role has been contested with later analyses and is still being studied (NCT02815410)²⁰. Its risk of emotional instability (aggression, depression or irritability) is about the same 5-13% risk as in non-brain tumor patients, with a reported 0.4% incidence of psychosis 4 weeks after initiating LEV^{67,69}.

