5.2.8 Clinical Experience

In our institution's experience, peri-operative LEV prophylaxis at a dose of 500mg BID was well tolerated among patients, with a 10% rate of AEs, mainly irritability, agitation and fatigue. At that dose, there was not a statistically significant reduction in post-operative seizure rates (34.6% seizure rate at this dose of LEV) among patients with newly-diagnosed high-grade gliomas (Pro00047350 Descriptive and Cost Analysis of Post-Operative Anti-Epileptic Drugs in Malignant Glioma). However, subsequent to the year studied, patients were initiated on 1000mg BID.

The goal of this study is to evaluate the impact of LCM, LEV or no AED on the re-admission rate and number of emergency room visits in the post-procedure period. If the use of an AED is shown to be beneficial, it is possible that LCM could be a preferable alternative for some patients, especially for those who do not tolerate LEV due to the behavioral side effects.

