Doses will be either LCM 100mg twice a day (BID) (Arm A), LEV 1000mg BID (Arm B), or no AED (Arm C). If a patient is randomized to Arm C and undergoes tumor mapping, the patient is allowed to receive one dose of AED in the operating room. If a patient is randomized to Arm A or Arm B and takes the morning dose of their AED, they do not need an intra-operative dose of AED. If a patient has a seizure during the post-procedure period, AEDs will be adjusted at the discretion of the treating physician. However, if a patient has intolerable side effects, patients will be changed to a different dose of the same medicine before consideration of another AED [i.e., BID to four times a day (QID) dosing if patient experiences diplopia on LCM].

Patients with high-grade tumors (newly-diagnosed or transformed) will be treated with standard radiation and temozolomide therapy per the Stupp protocol^{25,70}. For these patients, an AED taper will be initiated at the first clinic visit after completion of radiation. For patients with a low-grade tumor or recurrent disease of any grade, an AED taper will be initiated at the first scheduled post-procedure visit, approximately 6-10 weeks after the operation. LCM will be tapered by 100mg a week one week at a time. LEV will be tapered 500-1000mg one week at a time.

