7.1.3 Post-procedure data collection

Approximately 6-10 weeks after the procedure (for LGG or recurrent high grade glioma or brain metastasis) or first visit after radiation [for newly-diagnosed or transformed high grade glioma (HGG)], the following data will be obtained: admission duration for the MSR, any seizure activity, any readmissions, ED visits, and provider communications (telephone, email, and additional clinic encounters, etc.), as well as for tolerance of the AED by clinical history and neurological examination. Reasons for readmission and ED visits will also be noted. All of these data are only obtained if relevant during the 30-day post-procedure time. Patients will be provided a physical calendar to document any of the above, or provided access to the Research Electronic Data Capture™ (REDCap™) calendar, based on the patient's preference.

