13.5 Secondary objectives

This study has one secondary objective which is to assess the safety and tolerability of LCM and LEV.

Adverse events will be assessed according to the NCI Common Toxicity Criteria for Adverse Events (CTCAE) version 4. For each type of toxicity, the maximum grade experienced by the patient will be summarized with frequency distributions based upon all AESIs. Of particular interest are those adverse events of special interest (AESI), as defined in section [7.1.4](#), that occur within 30 days after MSR.

The percentage of patients experiencing any grade adverse events of special interest within 30 days of MSR will be summarized in each of the 3 treatment arms, and compared using chi-square tests. If AED is shown to have fewer re-hospitalizations or ED visits, then a pairwise comparison of LCM and LEV is of particular interest.

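### The closed AESI list omits diplopia, a leading lacosamide toxicity, and nothing outside that list is collected, so the safety analysis cannot report it

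*Protocol*

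**What the plan says.** **What is collected.** Protocol 11.1 and 11.1.1 carry the same rule: "Adverse events which are not an AESI will not be collected". Section 7.1.4 gives the list. It opens with seizure, dizziness, somnolence and cognitive disturbance and continues "nausea, vomiting, ataxia, nystagmus, suicidal ideation, suicide attempt, anxiety, irritability, depression, psychosis and personality change (e.g. aggression". That makes 15 terms, with no open category. Neither diplopia nor headache is among them.

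**What is known about LCM.** Section 5.2.5 says "Dizziness, headache, nausea and diplopia were the most common in a pooled analyses of the trials", at 10% or more with doses of 200 to 600 mg/day combined. It adds that incidence appeared dose related. On brain tumour patients, 5.2.7 says "Its related side effects are the same as in non-brain tumor patients, mainly dizziness at high doses".

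**What the trial expects.** Section 7.1 allows a change in the dosing schedule for intolerable side effects. Its example is a move to four-times-daily "dosing if patient experiences diplopia on LCM".

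**What is analysed.** The protocol's one secondary objective is the safety and tolerability of LCM and LEV. Its endpoint (Table 1) is the percentage of patients with an AESI within 30 days of surgery. Section 13.5 adds the by-type tables: "For each type of toxicity, the maximum grade experienced by the patient will be summarized with frequency distributions based upon all AESIs". The periodic trend review in 11.1.1 draws on the same AESI database. SAP section 7, item 1 lists 13 event types, and diplopia is not one of them.

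**The concern.** A restricted adverse-event list is a legitimate choice for two marketed drugs, provided that it covers the events each drug is best known for. Here it does not. The protocol treats diplopia as a leading LCM toxicity in its background and as a reason to alter dosing in its treatment rules, and then excludes it from the safety data.

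At stake is the protocol's only secondary objective. Section 13.5 singles out the LCM-LEV comparison if prophylaxis proves beneficial, and 5.2.8 suggests that LCM might then suit some patients better. A clinician making that choice would want to know how often LCM caused double vision at the trial dose. The trial as written cannot say.

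**Working it through.** **1. Size of the LCM arm.** Section 13.8 plans 232 patients, from 12% vs 25%, one-sided alpha 0.05, 80% power and one interim look. This reproduces. With unpooled variance 0.12 × 0.88 + 0.25 × 0.75 = 0.2931 and 116 per group, the standardised difference at full information is 0.13 / √(0.2931/116) = 2.59. Under the boundaries in 13.7 (2.31015 and 0.48887 at the interim, 1.63351 at the end), the overall alpha is 0.0500 and power is 0.803. The smallest total that reaches 80% is 232 (238 with pooled variance). Allocation is 1:1:2, so the LCM arm has 232 / 4 = 58 patients, with 29 expected at the interim.

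**2. Cases that would go untabulated.** The figure of 10% or more in 5.2.5 pools 200 to 600 mg/day. The trial gives 100 mg twice daily, the bottom of that range, and incidence appeared dose related. The rate r at 200 mg/day is therefore assumed. Expected cases are 58 × r, and the chance of at least one is 1 − (1 − r)^58.

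| Assumed r | Expected of 58 | Expected of 29 (interim) | Chance of at least one in 58 | Rows for diplopia in 13.5 |
|---|---|---|---|---|
| 3% | 1.7 | 0.9 | 83% | none |
| 5% | 2.9 | 1.5 | 95% | none |
| 10% | 5.8 | 2.9 | 99.8% | none |

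The last column follows from the collection rule and does not depend on r.

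**3. Could another route supply the count?**
- Section 7.1.3 asks about tolerance: "as well as for tolerance of the AED by clinical history and neurological examination". No analysis in section 13 uses it, and 11.1 bars recording diplopia as an adverse event.
- Section 13.6.5 and SAP section 7, item 5 describe AED changes. A schedule change for diplopia would appear there as a modified prescription, but the SAP variables listed do not include a reason.
- Immediate reporting under 11.2.1 is for events that are both serious and unexpected. Diplopia on LCM is expected and would usually not be serious.

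None of these yields a diplopia count by arm.

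**4. Effect on the any-AESI comparison.** Suppose that the drugs are truly equal and 40% of patients in each arm have some AESI (assumed). Suppose also that diplopia is independent of the listed events. The share of LCM patients missed is then u = r × (1 − 0.40) = 1.8, 3.0 or 6.0 percentage points for the three rates. Exact enumeration of two binomials (58 and 58, pooled test, |Z| > 1.96) gives the chance of a significant result favouring LCM. It is 0.024 when nothing is missed.

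| Share of LEV patients missed | r = 3% | r = 5% | r = 10% |
|---|---|---|---|
| 0 | 0.037 | 0.050 | 0.095 |
| 0.5u | 0.030 | 0.035 | 0.051 |
| u | 0.024 | 0.024 | 0.025 |
| 1.5u | 0.019 | 0.016 | 0.011 |

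The tilt towards LCM in the first row disappears in the third and reverses in the fourth. The documents do not say which row applies.

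**The case against.** Three objections have force.

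*Absent is not zero.* A reader might infer that the report will show diplopia in 0 of 58 LCM patients, and so imply that it is rare. The documents do not support this. Section 13.5 tabulates AESI types, so an event off the list has no row. The defect is silence on a known toxicity, not a false zero.

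*The between-drug bias is not established.* A reader might also infer that leaving out an LCM event flatters LCM against LEV. That needs a diplopia rate at 200 mg/day, a background AESI rate, little overlap with listed events and no matching loss on LEV. The documents supply none of these. Patients with diplopia who also have dizziness, ataxia, nausea or nystagmus are already counted. LEV has gaps of its own: 5.2.8 describes the institution's LEV adverse events as "mainly irritability, agitation and fatigue", and neither agitation nor fatigue has its own AESI term. This objection stands in full.

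*Intolerable diplopia would leave a trace.* It could show up in AED changes, provider communications or reasons for an ED visit. That is true, but it gives no rate, and milder cases would leave less trace or none.

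What these objections leave untouched is the collection rule itself, which excludes an event that the protocol expects.

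**Conclusion.** The point holds as a gap in the safety data. Followed as written, the plan cannot report diplopia on either drug, in the by-type tables, in the any-AESI endpoint or in the trend review. That conclusion rests on the wording of 7.1.4, 11.1, 11.1.1 and 13.5 and on the visible SAP list, and needs no assumption about rates. The size does need one: roughly 2 to 6 LCM patients out of 58 at assumed rates of 3 to 10%.

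The direction and size of any effect on the LCM-LEV any-AESI comparison are undetermined. The primary endpoint is not affected.

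Two smaller matters sit beside this. Headache, also among the four events in 5.2.5, is uncollected too. Nystagmus is on the 7.1.4 list but has no variable in SAP section 7, item 1. That is only an alignment gap, because 7.1.4 and 11.1 already require it in the adverse-event case report form.

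**What to change.** **If collection is still open:** add diplopia to Protocol 7.1.4, to the patient questionnaire and to SAP section 7, item 1. Give it the same yes/no, severity and medical-attention fields as the other events, ask it in all three arms, and count it in the any-AESI endpoint. The cost is one AESI term and one more item to collect, with no added patients or visits.

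**If collection has ended**, as the past tense in SAP section 4 suggests: state in the report that diplopia and headache were not collected, and do not rank LCM above LEV on the any-AESI percentage alone. The cost is a sentence or two.

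**In either case:** list nystagmus in SAP section 7, item 1, to match Protocol 7.1.4.
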